9.4 Vital Signs

Blood pressure, respiratory rate, heart rate and oral temperature will be measured in a sitting position after at least 5 minutes of sitting (except for safety reasons) at screening, at check-out on Day 4 and at study exit. Blood pressure, heart rate, and oral temperature will also be measured prior to dosing and approximately 2, 4, 24 and 48 hours post-dose.

Descriptive statistics (mean, median, SD, Min, Max, and sample size) will be presented by group and overall for screening, 2, 4, 24 and 48 hours post-dose and study exit for each vital sign measurement. Baseline will be defined as the last results (scheduled or unscheduled) obtained prior to the administration of ELX-02. Unscheduled results will not be included in the summary tables except for baseline calculation if applicable. Change from baseline descriptive statistics for post-dose measurements as well as for study exit will be presented. Results from repeat tests will not be included in the summary statistics unless the repeat was required (and documented as such) due to technical reasons or an invalid initial result.

A listing of all vital signs results will be provided by subject.

9.5 Electrocardiogram

Supine ECG will be performed at screening, prior to dosing, approximately 2 hours post-dose, at check-out on Day 4 and at study exit. The quantitative ECG measurements are heart rate (HR), PR interval, QRS interval, QT interval, QTcB (Bazett's formula correction) and QTcF (Fridericia formula correction).

Descriptive statistics (mean, median, SD, Min, Max, and sample size) will be presented by group and overall for screening, pre-dose, 2 hours post-dose at check-out on Day 4 and study exit for each ECG measurement. Baseline will be defined as the last results (scheduled or unscheduled) obtained prior to the administration of ELX-02. Unscheduled results will not be included in the summary tables except for baseline calculation if applicable. Change from baseline descriptive statistics for post-dose measurements as well as for study exit will be presented. Results from repeat tests will not be included in the summary statistics unless the repeat was required (and documented as such) due to technical reasons or an invalid initial result.

A listing of all ECG results will be provided with the abnormal values flagged. In addition, a listing of significant ECG findings will be provided.

9.6 Injection Site Evaluation

Local reactions at the injection site will be evaluated by a trained observer and recorded: prior to study drug injection, approximately 0.75, 2, 6, 12, 24, 36, 48, and 72 hours post-dose, and at study exit. The severity of each local reaction at the injection site will be graded according to the NIH Division of AIDS (DAIDS) criteria presented in Table 9-1.

Eloxx Pharmaceuticals

Table 9-1 Site Reactions to Injections and Infusions DAIDS Grading Table

Parameter	GRADE 1 MILD	GRADE 2 MODERATE	GRADE 3 SEVERE	GRADE 4 POTENTIALLY LIFE- THREATENING
Injection Site Pain or Tenderness	Pain or tenderness causing no or minimal limitation of use of limb	Pain or tenderness causing greater than minimal limitation of use of limb	Pain or tendemess causing inability to perform usual social and functional activities	Pain or tenderness causing inability to perform basic self-care function OR hospitalization indicated
Injection site Erythema or Redness	2.5 to <5 cm in diameter OR 6.25 to <25 cm2 surface area AND symptoms causing no or minimal interference with usual social and functional activities	≥5 to <10 cm in diameter OR ≥25 to <100 cm2 surface area OR Symptoms causing greater than minimal interference with usual social and functional activities	≥10 cm in diameter OR ≥100 cm2 surface area OR ulceration OR secondary infection OR phlebitis OR sterile abscess OR drainage OR symptoms causing inability to perform usual social and functional activities	Potentially life- threatening consequences (e.g., abscess, exfoliative dermatitis, necrosis involving dermis or deeper
Injection site Induration or Swelling	to <5 cm in diameter OR 6.25 to <25 cm2 surface area AND symptoms causing no or minimal interference with usual social and functional activities	≥5 to <10 cm in diameter OR ≥25 to <100 cm2 surface area OR Symptoms causing greater than minimal interference with usual social and functional activities	≥10 cm in diameter OR ≥100 cm2 surface area OR ulceration OR secondary infection OR phlebitis OR sterile abscess OR drainage OR symptoms causing inability to perform usual social and functional activities	Potentially life- threatening consequences (e.g., abscess, exfoliative dermatitis, necrosis involving dermis or deeper tissue)
Injection site Pruritis	Itching localized to the injection site that is relieved spontaneously or in <48 hours of treatment	Itching beyond the injection site that is not generalized OR itching localized to the injection site requiring ≥48 hours treatment	Generalized itching causing inability to perform usual social and functional activities	NA

The number of subjects (frequency and percentage) will be tabulated for each individual parameter and reaction grading by time point of collection.

10. Pharmacokinetic Analyses

10.1 Handling of the Below the Lower Limit of Quantification (BLQ) and the No Reportable Concentration Values

When handling the below the limit of quantification (BLQ) data the following rules will apply for the derivation of PK parameters:

Eloxx Pharmaceuticals

- Concentration values below the assay's limit of quantification (BLQ) for pre-dose samples will be treated as zero.
- Post-dose BLQ values prior to the first quantifiable concentration will be treated as zero.
- Post-dose BLQ values after the first quantifiable time point that are not followed by measurable concentration will be set to missing.
- The sampling times relative to dosing for pre-dose samples will also be treated as zero.

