### 12.1 Pharmacokinetics

#### 12.1.1 Plasma Pharmacokinetic Parameters

The following PK parameters will be calculated by standard non-compartmental methods with ELX-02 plasma concentrations:

- 1)  $AUC_{0-72}$ : area under the concentration-time curve from time zero to 72 hours post-dose. Whenever concentration data is missing for the 72-hour post-dose sample for a subject, calculation of the  $AUC_{0-72}$  must not be done.
- 2)  $AUC_{0-t}$ : area under the concentration-time curve from time zero to the last non-zero concentration
- 3)  $AUC_{0-\infty}$ : area under the concentration-time curve from time zero to infinity (extrapolated)
- 4)  $C_{max}$ : maximum observed concentration
- 5) Residual area: calculated as  $100 * (1 - AUC_{0-t} / AUC_{0-\infty})$
- 6)  $T_{max}$ : time of observed  $C_{max}$
- 7)  $T_{1/2 el}$ : elimination half-life
- 8)  $K_{el}$ : elimination rate constant
- 9)  $CL/F$ : apparent total clearance (L/hr) estimated from dose/ $AUC_{0-\infty}$
- 10)  $V_d/F$ : apparent volume of distribution (L) estimated from  $CL/K_{el}$  ( $\beta$ )

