6.2 Pharmacokinetic Population

The PK population will include all subjects completing the study and for whom the PK profile can be adequately characterized.

Any subject with ELX-02 pre-dose concentration prior to ELX-02 administration on Day 1 will be presented in the listings of concentrations and pharmacokinetic data but excluded from the descriptive statistics and analysis of variance (ANOVA) tables if the pre-dose concentration is greater than 5% of the C_{max} value measured on Day 1 for that subject. Subjects withdrawn due to AEs or PK reasons will be analyzed and reported but excluded from the statistical analysis. However, the concentrations for these subjects will be included in the descriptive statistics.

Here are some aspects to be considered (but not to be limited to) when determining data availability for the PK population: inclusion and exclusion criteria, acceptable times for visit dates and measurements, compliance with treatment, the nature and quality of the data, withdrawal, and any protocol deviation. The final responsibility of deciding which subjects are to be included or excluded lies with the principal investigator and/or the Sponsor.

Following to the end of the clinical portion of the study, prior to the start of the analysis of the samples, subjects analysed for PK population will be established by the inVentiv Health project team and finalized after Sponsor's review, according to the SOP ANI 3550_4 (Use of the Confinement Report and Subjects To Be Analyzed Form). All information including: subject withdrawals, adverse events that could affect characterization of the PK profile, concomitant medications taken, deviations to dosing procedures, deviations to study restrictions and sample particularities/missing blood draw will be detailed in the Confinement Report and Subjects To Be Analyzed Form (CR/STBA form).

Eloxx Pharmaceuticals

7. Interim Analyses

No formal interim analysis was planned in the protocol. However, interim PK analyses will be conducted after completion of dosing of the mild (Group 1) and moderate (Group 2) RI patients in order to assess plasma and urine ELX-02 exposure prior to proceeding with administration to severe (Group 3) RI patients. In interim analyses, PK parameters will be calculated using scheduled sampling times as actual sampling times will not be available.

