10.3 Pharmacokinetic Parameters

10.3.1 Plasma Pharmacokinetic Parameters

For Group 1 to 4, a total of 13 blood samples will be drawn from each subject for quantitation of ELX-02 for pharmacokinetic analyses: 0.250, 0.500, 0.750, 1.00, 2.00, 4.00, 6.00, 12.0, 24.0, 36.0, 48.0, 72.0, and 168 hours post-dose.

Plasma ELX-02 concentrations data will be used to calculate the following parameters by standard non-compartmental methods:

 AUC_{0-24} : Area under the concentration-time curve from time zero to 24 hours post-dose.

Whenever concentration data is missing for the 24-hour post-dose sample for a

subject, calculation of the AUC₀₋₂₄ must not be done.

 AUC_{0-72} : Area under the concentration-time curve from time zero to 72 hours post-dose.

Whenever concentration data is missing for the 72-hour post-dose sample for a

subject, calculation of the AUC₀₋₇₂ must not be done.

AUC_{0-t}: Area under the concentration-time curve from time zero to the last non-zero

concentration, calculated using the linear trapezoidal method.

AUC_{0-inf}: Area under the concentration-time curve from time zero to infinity

(extrapolated), calculated as $AUC_{0-t}+C_t/K_{el}$, where: C_t = the last observed

non-zero concentration.

Eloxx Pharmaceuticals

C_{max}: Maximum observed concentration.

Residual area Residual area, calculated as 100*(1- AUC_{0-t} / AUC_{0-inf}).

 T_{max} : Time of observed C_{max} .

 $T_{\frac{1}{2} \text{ el}}$: Elimination half-life, calculated as $\log(2)/K_{\text{el}}$ using the natural logarithm.

K_{el}: Elimination rate constant. This parameter will be the negative of the

estimated slope of the linear regression of the log-transformed concentration (natural logarithm) versus time profile in the terminal elimination phase. At least 3 concentration points will be used in estimating K_{el} . The time point where log-linear K_{el} calculation begins $(K_{el\ Lower})$, and the actual sampling time of the last quantifiable concentration used to estimate the K_{el} $(K_{el\ Upper})$ will be reported with the correlation coefficient from the linear regression to

calculate Kel.

CL/F: Apparent total body clearance, calculated as Dose/AUC_{0-inf}.

V_d/F: Apparent volume of distribution, calculated as Dose/(K_{el} x AUC_{0-inf}).

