The ELX-02 plasma and urine concentrations, safety and tolerability data will be received as SAS^{\circledast} datasets from the inVentiv data management facility. Screening failures and ineligible volunteer's data (subject disposition) will be received from the clinical site as source data.

Eloxx Pharmaceuticals

13. Handling of Missing Data

For PK, only observed data will be used in the data analysis except for concentration values BLQ and samples with no reportable value occurring prior to dosing as described in Section 10.1. No attempt will be made to extrapolate or interpolate estimates for missing data.

For safety,

- If an AE is recorded with an onset date corresponding to a dosing day, but the time is missing, then the AE will be assigned to the treatment as a TEAE.
- If an AE is recorded with an onset date that does not correspond to the dosing day, but the time is missing, then the AE will be assigned to the treatment as a TEAE if AE onset date is after dosing date.
- If an AE is recorded with an onset date where day and time are both missing, then the AE allocation to the treatment will be done on a case by case basis considering available information (e.g. AE end date, AE comments, subject disposition).

Eloxx Pharmaceuticals

14. Software to be Used

PK analysis will be performed using Phoenix WinNonlin® version 8 or higher, which is validated for bioequivalence/bioavailability studies by inVentiv. The safety data tables and listings, as well as PK tables and listings will be created using $SAS^{\textcircled{R}}$, release 9.2 or a higher version. PK figures will be created using R (version 3.5). The PK report text will be created using Microsoft® Office Word 2010, or a higher version.

Eloxx Pharmaceuticals

15. Reference List

None.

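### Read literally, the SAP's BLQ and missing-sample rules together bar AUC0-72 in essentially all controls and may remove AUC0-24 selectively in fast-eliminating controls

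*SAP*

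**What the plan says.** SAP 10.1 introduces its BLQ rules with "the following rules will apply for the derivation of PK parameters". One of them is "Post-dose BLQ values after the first quantifiable time point that are not followed by measurable concentration will be set to missing".

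SAP 10.3.1 defines the partial areas. For AUC0-24: "Whenever concentration data is missing for the 24-hour post-dose sample for a" subject, the area is not to be calculated. The same prohibition is attached to AUC0-72: "Whenever concentration data is missing for the 72-hour post-dose sample for a" subject. The sentence comes from Protocol 12.1.1 ("Whenever concentration data is missing for the 72-hour post-dose sample for a subject, calculation of the" AUC0-72 is barred), but the protocol has no BLQ rule. The two provisions meet only in the SAP.

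SAP 13 allows only observed PK data, "except for concentration values BLQ and samples with no reportable value occurring prior to dosing as described in Section 10.1", and adds: "No attempt will be made to extrapolate or interpolate estimates for missing data". Its BLQ exception therefore leads back to SAP 10.1.

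Several analyses depend on these areas:
- SAP 4 and 5 make AUC0-24 primary and keep AUC0-72 as secondary.
- SAP 10.4 requires ratios to Control with 90% CIs for both, and lists both for the regression on renal function.
- SAP 10.3.2 computes CL_R as Ae0-24/AUC0-24.
- SAP 7 promises interim summaries of all primary and secondary PK parameters for the mild and moderate groups.

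**The concern.** A BLQ result is an observation: the sample exists and the concentration is known to be low. If SAP 10.1 turns it into a missing value and SAP 10.3.1 then forbids the partial area, the area is lost because the drug has been cleared. That happens most in subjects with normal renal function, who form the denominator of every ratio.

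There are two consequences. AUC0-72 could be absent in the control group, which leaves its three ratios without a denominator and the regression without values at the normal end. AUC0-24 could be absent in just those controls who eliminate fastest. The retained control mean would then be too high and the impaired/Control ratios too low, understating the effect that the study is meant to measure.

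**Working it through.** **Inputs.** Protocol 5.2.2.2, 1 mg/kg SC, N=6: Cmax 3576 ng/mL at 1.0 h, t½ 2.14 h, CL/F 5.50 (SD 0.349) L/h, AUC0-12 13,131 (SD 1729) ng·h/mL. Protocol 5.1.2: mean t½ of 2 to 4 h for 0.3-5.0 mg/kg, with monophasic decline at the lowest doses. The documents give neither an LLOQ nor a loss rate; LLOQ values below are assumptions.

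**Coherence check.** A triangle to Cmax plus mono-exponential decline gives AUC0-12 = 3576/2 + (3576/k)(1 − 2^(−11/2.14)) = 12,515, with k = ln2/2.14. The protocol states 13,131, so the figures agree well enough to project concentrations.

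**72 h.** C(72) = 3576 × 2^(−71/t½) gives 4e-7, 3e-4 and 0.016 ng/mL at t½ 2.14, 3 and 4 h. A quantifiable value needs t½ = 71·ln2/ln(3576/LLOQ), which is 4.1 h at LLOQ 0.02, 4.7 h at 0.1 and 6.0 h at 1 ng/mL.

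**24 h.** C(24) = 3576 × 2^(−23/t½) gives about 2.1 ng/mL at 2.14 h and 66 ng/mL at 4 h. The outcome therefore depends on the LLOQ.

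**Between-subject spread.** One-compartment model with CL/F 5.5 L/h, dose 5.5 × 13.131 = 72.2 mg (assumed), ka set so that Tmax is 1 h, and 400,000 simulated subjects per cell. CL CV is 6.3% (0.349/5.50) or 13.2% (1729/13131); V CV is 10% (assumed). Ranges span the two CL CVs.

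Controls losing AUC0-72:
- LLOQ 1: 99.9-100% over 2.14-4 h.
- LLOQ 0.1: 99.9-100% up to 3 h, 91-97% at 4 h (0.2-0.5 of 6 kept).
- LLOQ 0.02: 98-100% up to 3 h, 66-72% at 4 h.

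Controls losing AUC0-24 and CL_R, and the resulting inflation of the retained control geometric mean AUC:

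| t½ | Lost, LLOQ 1 / 2 / 5 ng/mL | Inflation, LLOQ 1 / 2 / 5 |
|---|---|---|
| 2.14 h | 20-28% / 48-49% / 78-88% | 1-5% / 3-9% / 6-16% |
| 2.5 h | 2-8% / 10-19% / 47-48% | 0.2-2% / 0.7-4% / 3-9% |
| 3 h | at most 1% / 3% / 15% | at most 0.2% / 0.8% / 3% |
| 4 h | at most 0.5% | at most 0.2% |

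For impaired groups, elimination was scaled to eGFR with a renal share of CL of 85-100%. At a control t½ of 2.14 h, mild subjects lose AUC0-24 in 0.3-3% / 2-8% / 13-24%, and moderate and severe in under 0.5%. Mild subjects lose AUC0-72 in 81-100% at LLOQ 1.

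**Sensitivity.** V CV of 5-20% changes the 2.14 h loss to 11-34% / 47-49% / 72-95% and the inflation to 1-6% / 2-10% / 3-20%. The model's Cmax (3,075 at 2.14 h, lower at longer t½) falls short of 3576. Rescaling C(24) to the simple path leaves 2.14 h unchanged and lowers the loss at 2.5 h to 1-6% / 7-16% / 39-42%. A separate model (15% CV on the elimination rate, fixed volume, eGFR 105 for control and 75 for mild) moves Mild/Control AUC0-24 from 1.39 to 1.31, 1.26 and 1.17 at LLOQ 1, 2 and 5.

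**Precision.** The 90% CI half-width is proportional to t(0.95, n1+n2−2) × √(1/n1+1/n2). Going from 6 vs 6 to 6 vs 3 widens it by 28%, and to 6 vs 5 by 6%. With 8 controls of whom 3 are lost (6 vs 8 to 6 vs 5), it widens by 15%.

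**Tail conventions.** Typical control at t½ 2.14 h, last quantifiable at 12 h, linear trapezoid on the SAP times (ng·h/mL):
- AUC0-t 13,438; AUC0-inf 13,752.
- AUC0-24 with the measured 24-h value (2.09 ng/mL): 14,061.
- AUC0-24 with BLQ as zero: 14,049, 0.1% below the measured-value trapezoid.
- AUC0-24 with Kel extrapolation: 13,746, 2.2% below it.

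The model's true AUC is 72.2/5.5 = 13,127 after unit conversion. Against it the three run 7.1%, 7.0% and 4.7% high, so the trapezoid is not a standard of truth. Under the zero rule the last piece is 6 × C12, against C12/Kel in AUC0-inf. AUC0-24 therefore exceeds AUC0-inf whenever t½ is below 6·ln2 = 4.2 h: by 2.2% at 2.14 h, 2.6% at 2.5 and 3 h, and 0.5% at 4 h.

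**The case against.** The best counter-argument is that missing in SAP 10.3.1 was meant as not drawn or not reportable. The sentence was carried over from a protocol without a BLQ rule. SAP 6.2 uses the word for blood draws ("sample particularities/missing blood draw will be detailed in the Confinement Report and Subjects To Be Analyzed Form"). The heading of SAP 10.1 and SAP 13 both name BLQ and non-reportable samples as separate categories. SAP 10.3.2 also expects that some parameters will not be calculable and promises explanations, so an absent AUC0-72 would not pass silently. This stands as a plausible account of intent, but no section states it. SAP 10.1 expressly covers parameter derivation, and explaining a gap does not undo selective loss. Two competent analysts could build different datasets.

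It is also fair that AUC0-72 is secondary and that in controls it adds almost nothing to AUC0-inf, which remains primary.

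The AUC0-24 effect is undetermined: it runs from nothing to most of the control group, depending on an LLOQ that the documents do not give. The protocol also prints a half-life SD of 2.14 h, equal to the mean and possibly a misprint. Taken at face value, a control near 6.5 h would have about 1.8 ng/mL at 72 h. That could leave a stray AUC0-72 value, though not a usable comparison.

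A reader might infer that the primary analysis fails, or that the AUC0-24 ratios will certainly be biased. The documents support neither: AUC0-t, AUC0-inf, Cmax, Tmax, Ae0-t and Rmax do not use the barred areas.

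**Conclusion.** The concern holds for the SAP as worded and should be fixed before PK parameters are derived. Under the literal reading, AUC0-72 is lost in essentially all controls at the reported 2-4 h half-lives, so SAP 10.4 orders ratios that SAP 10.1 and 10.3.1 prevent. The exception is a corner with both a long half-life and a very low LLOQ (4 h with 0.02 ng/mL), where about a third of controls would keep a value.

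For AUC0-24 and CL_R the conclusion is only that selective loss in controls is possible. Where it occurs, it pushes the impaired/Control AUC0-24 ratios downward. The control mean is inflated by less than 1% at t½ of 3 h or more with LLOQ of 2 ng/mL or less, and by 3-16% at 2.14 h with LLOQ 2-5 ng/mL. These sizes rest on an assumed LLOQ, assumed variability in V, one-compartment decline and an assumed dose. A slow phase still above the LLOQ at 24 h would reduce the loss. The primary objective survives.

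**What to change.** In SAP 10.3.1, limit the prohibition to samples that were not collected or have no reportable result. State that a BLQ result at 24 h or 72 h does not bar the partial AUC. Add the matching exceptions to SAP 10.1 and SAP 13, and state the LLOQ.

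Pre-specify one tail convention, the same in all groups and fixed before PK derivation:
- **Kel extrapolation:** AUC0-t plus the extrapolated area to 24 h or 72 h. This keeps the partial area at or below AUC0-inf, but creates a step of about 2% against a measured 24-h value in a typical control at t½ 2.14 h.
- **Zero:** trailing BLQ set to zero under the linear trapezoid, for the partial areas only. This avoids the step, but the SAP must disclose that AUC0-24 and AUC0-72 can exceed AUC0-inf by about 0.5-2.6% when the 24-h value is BLQ.

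Report the other convention as a sensitivity analysis. Either is defensible; what matters is that the choice is made before anyone sees which controls are BLQ.

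The cost is SAP wording and one software setting, with no new data. The tail approximation is about 2% or less relative to the measured-value trapezoid in a typical control at t½ 2.14 h.

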10.2 Handling of the Difference between the Scheduled and the Actual Sampling Times

The actual clock time for dosing and the actual clock time for each collection time for the PK samples will be recorded using electronic data capture. For all sampling times, the actual sampling times will be calculated as the difference between the sample collection actual clock time and the actual clock time of dosing. The actual post-dose sampling times expressed in hours and rounded off to three decimal digits will be used to calculate the PK parameters, except for pre-dose samples occurring prior to dosing, which will always be reported as zero (0.000), regardless of the time difference. Scheduled sampling times will be presented in concentration tables and mean graphs, while actual sampling times will be presented in the individual graphs in the PK section of the report. A listing of the actual times for PKs will be provided for PK samples.

